5.7.3 Additional Assessments

5.7.3.1 Sample Collection

Samples for genomic or other omic biomarker assessment will be collected at the following time points:

- Buffy coat: Day 1 (Pre-dose)
- Urine Sample Collection: Screening, Day -1 (check-in), Day 1 (pre-dose and 24 hours), and Days 7, 28, 56, and 84

All of these samples will be collected in the fasted state.

These samples will be used for analyses that will be considered hypothesis-generating and exploratory. All sample analysis will be performed by DARS staff.

5.7.3.2 Specimen Handling

A buffy coat from each study participant will be used for exploratory genomic analyses. On the specified collection day/time (Day 1, pre-dose), 5 mL of whole blood sample will be processed for plasma and the upper plasma phase will be transferred to a new sterile Falcon tube without disturbing the intermediate buffy coat layer. The buffy coat layer will then be transferred to a sterile 2 mL Eppendorf (safe-lock) tube (on wet ice). Buffy coat samples should be immediately frozen in a dry ice/ethanol bath (for ~ 40 seconds) and then transferred to a -80°C freezer. Only sterile (nuclease-free) plastic pipettes, pipette tips and tubes should be used. All barcoded buffy coat Eppendorf tubes should be frozen and stored at -80°C as described above until appropriately transported to the FDA for long-term storage. Sample analysis will be performed by DARS research staff.

At specified times for urine sample collection, 3-5 mL of urine will be processed according to the SOP, separated into 6 approximately equal aliquots, immediately frozen in a dry ice/ethanol bath (for ~40 second or until frozen), and then immediately transferred to -80°C for long-term storage. Sample analysis will be performed by DARS staff.

5.7.4 Safety Assessments

Safety will be evaluated in terms of AEs, clinical laboratory results (hematology, serum chemistry, and urinalysis), vital sign measurements (blood pressure, heart rate, respiratory rate, and oral body temperature), safety 12-lead ECG results, and physical examination findings.

5.7.4.1 Adverse Events

5.7.4.1.1 Adverse Event Definitions

An AE is defined as any untoward and/or unintended sign, including an abnormal clinical laboratory finding, symptom, or disease temporally associated with the use of a study drug, whether or not considered related to the study drug. Events or conditions that increase in frequency or severity during or as a consequence of use of a drug in human clinical trials will also be considered AEs.

A treatment-emergent adverse event (TEAE) is defined as an AE that begins after study drug administration.

An unexpected AE is any AE having a specificity or severity not consistent with the current investigator's brochure for the study drug(s).

A serious adverse event (SAE) is defined as any AE occurring at any dose that meets the following criteria:

- Results in death,
- Is life threatening,
- Requires hospitalization or prolongation of existing hospitalization,
- Results in persistent or significant disability or incapacity,
- Results in a congenital anomaly/birth defect due to exposure prior to conception or during pregnancy, or
- Is an important medical event that may not meet the previous criteria but, based upon appropriate medical judgment, jeopardizes the subject or requires medical or surgical intervention to prevent one of the outcomes listed previously.

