The safety population will include all subjects who receive at least 1 dose of any of the study drugs. All AEs will be coded using the Medical Dictionary for Regulatory Activities (MedDRA). The incidence of AEs, organized by system organ class and preferred term, will be summarized with a focus on treatment-emergent AEs. Vital sign measurements will be summarized using descriptive statistics by time point. All values will be evaluated for clinically notable results. Data for additional safety parameters (e.g., physical examination findings) will be listed.

Date of Protocol:

18 May 2020

1. List of Abbreviations

Abbreviation	Definition
AE	adverse event
Ag/Ab	antigen/antibody
ANCOVA	analysis of covariance
ApoB	Apolipoprotein B
AUC	area under the concentration-time curve
AUEC	area under the effect curve
pAUEC	percentage area under the effect curve
CFR	Code of Federal Regulations
C_{max}	maximum observed concentration
COVID-19	coronavirus disease of 2019
DNA	deoxyribonucleic acid
EC ₅₀	the concentration that gives-half maximal response
ECG	electrocardiogram
eCRF	electronic case report form
E_{max}	maximum PD response
FDA	Food and Drug Administration
GCP	Good Clinical Practice
HBsAg	hepatitis B surface antigen
HepC	hepatitis C
HIPAA	Health Insurance Portability and Accountability Act
HIV	Human immunodeficiency virus
ICH	International Council for Harmonisation
IRB	Institutional Review Board
IV	intravenous
kg	kilogram
LDL-C	low-density lipoprotein (LDL) cholesterol
MedDRA	Medical Dictionary for Regulatory Activities
mg	milligram
NSAID	nonsteroidal anti-inflammatory drug
PBMC	peripheral blood mononuclear cell
PCSK9	Proprotein convertase subtilisin/kexin type 9
PD	pharmacodynamic
PK	pharmacokinetic
QA	quality assurance
RNA	ribonucleic acid
SAE	serious adverse event

SARS-CoV-2

severe acute respiratory syndrome coronavirus 2

SC

subcutaneously

SD

standard deviation

TEAE

treatment-emergent adverse event

 T_{max}

time of C_{max}

2. Introduction

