5.7.4.1.2 Adverse Event Reporting

The recording of AEs will begin after the subject signs the informed consent form and will continue until discharge (or early termination). All AEs, whether serious or nonserious and whether or not related to the study drug, must be recorded in the eCRF. Study subjects will be instructed to warn study staff if he or she has any unexpected symptoms. In addition, all subjects will receive a reminder telephone call approximately 24 hours before Check-in.

Any SAE (whether expected or unexpected) must be entered into the eCRF system and reported by facsimile to the medical monitor or designee using the SAE Reporting Form within 24 hours of the investigator or study clinic staff becoming aware of the event. It is the responsibility of the investigator to report all SAEs to the medical monitor, to provide the most complete report possible, and to assess each SAE for its relationship to the study drug. The investigator is responsible for obtaining follow-up information on all SAEs and submitting follow-up SAE data. Any unexpected SAEs must be reported promptly to the investigator's IRB as per the IRB's requirements.

In the event of a fatal or life-threatening SAE, the sponsor will notify the appropriate FDA authorities by telephone or facsimile within 7 calendar days of receipt of the report. The sponsor will follow all 7-day alert reports with a written report within 10 working days of receipt of the case. Serious AE cases that concern nonfatal, nonlife-threatening events that are unexpected and at least possibly related to the study drug will be submitted in writing to the FDA within 10 working days of receipt.

Furthermore, any AEs that are not expected, occur at a higher frequency, or would require modification of the study protocol and/or informed consent must be reported to the FDA within 10 working days.

Adverse events that are assessed by the investigator as possibly or probably related to the study drug will be followed until they resolve or stabilize. All SAEs will be followed until resolution.

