5.9.8 Safety Analyses

5.9.8.1 Adverse Events

All AEs will be coded using the latest version of the Medical Dictionary for Regulatory Activities. The incidence of TEAEs, organized by system organ class and frequency, will be summarized by seriousness, severity, relationship to treatment, and by treatment at onset of the TEAE. A detailed listing of serious AEs and TEAEs leading to withdrawal will also be provided.

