5.9.8.2 Clinical Laboratory Tests

Clinical laboratory results (hematology, serum chemistry, and urinalysis) will be summarized using descriptive statistics (number of subjects, mean, SD, minimum, median, and maximum). Clinical laboratory results will be classified as normal or abnormal, according to the reference ranges of the individual parameter. The number and percentage of subjects with abnormal laboratory results will be provided. No statistical testing will be performed on clinical laboratory data.

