7.7. Safety Analyses

7.7.1 Adverse Events

All AEs will be coded using the latest version of the Medical Dictionary for Regulatory Activities. The incidence of TEAEs, organized by system organ class and frequency, will be summarized by seriousness, severity, relationship to treatment, and by treatment at onset of the TEAE. A detailed listing of serious AEs and TEAEs leading to withdrawal will also be provided.

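### The TEAE definition tests onset only, so an adverse event recorded before dosing that worsens afterwards can be left out of the TEAE tables in protocol 5.9.8.1 and SAP 7.7.1

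*Protocol*

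**What the plan says.** Protocol 5.7.4.1.1 gives two tests. For an AE, the section adds to its basic definition: "Events or conditions that increase in frequency or severity during or as a consequence of use of a drug in human clinical trials" are also to be counted as AEs. For a TEAE, the test is the start of the event alone: "A treatment-emergent adverse event (TEAE) is defined as an AE that begins after study drug administration".

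Protocol 5.7.4.1.2 opens the recording window before dosing: "The recording of AEs will begin after the subject signs the informed consent form". Consent is taken at screening, which runs from Day -21 to Day -2. Dosing is on Day 1.

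Protocol 5.9.8.1 and SAP 7.7.1 plan the same AE summary: "The incidence of TEAEs, organized by system organ class and frequency, will be summarized by seriousness, severity, relationship to treatment", and also by treatment at onset. Both then add: "A detailed listing of serious AEs and TEAEs leading to withdrawal will also be provided". The SAP uses the term TEAE without defining it, either there or in its table of abbreviations.

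The safety paragraph under Statistical Methods in the protocol synopsis is broader: "The incidence of AEs, organized by system organ class and preferred term, will be summarized with a focus on treatment-emergent AEs".

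**The concern.** A treatment-emergent table is meant to show what happened to subjects after they received the drug, and worsening of something already present is part of that. Here the AE definition recognises worsening, but the definition that decides entry to the tables does not. Whether a worsened event is counted may then depend on how the site enters it. If the original record is updated and keeps its pre-dose onset, the event is not a TEAE. If a new record is opened at the worsening, it is. Neither document says which to do.

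What is at stake is the completeness of the TEAE counts by severity and relationship to treatment, and of the listing of TEAEs that led to withdrawal.

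**Working it through.** The plan gives no figure to reproduce. The check sets the definitions against the recording window and each safety summary, and then traces four cases.

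**Will pre-dose AE records exist?** Yes, the plan provides for them. AEs are monitored at screening (protocol 5.6.2) and at check-in (5.6.3.1). Physical examinations are done at both visits, and protocol 5.9.8.5 and SAP 7.7.5 have abnormal findings recorded as AEs.

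**Which definition governs the tables?** The SAP supplies none, so the onset-only sentence in protocol 5.7.4.1.1 applies to SAP 7.7.1 as well.

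**Case 1: an AE recorded between consent and dosing worsens after dosing.** As a hypothetical example, take back pain, which protocol 5.1.3 names as a common evolocumab reaction. It is recorded as mild at check-in and becomes severe on Day 3. The event began on Day -1, so under the literal test it is not a TEAE. It is missing from the incidence tables of protocol 5.9.8.1 and SAP 7.7.1 unless the site enters the worsening as a separate AE. An event with a pre-dose onset also has no treatment at onset under which to tabulate it.

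**Case 2: the same event is non-serious and leads to withdrawal.** The dedicated listing covers serious AEs and TEAEs leading to withdrawal. This event is neither serious nor, read literally, a TEAE, so it falls outside that listing. It remains in the general data listings (protocol 5.9.3, SAP 7), and the withdrawal and its reason remain in the disposition summary (protocol 5.9.4, SAP 7.1).

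**Case 3: a medical-history condition worsens after dosing.** Inclusion criterion 4 admits subjects with abnormal findings judged not clinically significant. If such a condition worsens, the AE definition makes it an AE. Dated at the worsening, it begins after dosing and is a TEAE. Dated at the start of the condition, it is not. No rule chooses between the two, so omission is possible but not established.

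**Case 4: summaries that do not use TEAE status.**
- The synopsis plans an incidence of AEs, which would include Case 1 if that table is produced. Neither protocol 5.9.8.1 nor SAP 7.7.1 carries it over.
- Protocol 5.9.8.2 counts laboratory abnormalities without reference to TEAE status: "The number and percentage of subjects with abnormal laboratory results will be provided". SAP 7.7.2 omits that sentence.
- The incidence of pathological ECG statements (protocol 5.9.8.4, SAP 7.7.4) is likewise independent of TEAE status.
- Laboratory and ECG summaries would not capture a symptom such as back pain.

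**The case against.** The strongest reply is that the sentences in 5.7.4.1.1 can be read together. Worsening is itself an AE, and protocol 5.7.4.1.2 requires every AE to be recorded. On that reading the worsening is a new AE that begins after dosing and is therefore a TEAE as written. This is a reasonable reading, and for medical-history conditions it is a natural one. It does not settle Case 1, because nothing requires a new record or a new onset date when an AE that is already open gets worse.

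Three stronger readings are tempting, and the documents do not support them.
- A reader might infer that such events vanish from every safety incidence table. They do not: the synopsis plans an all-AE incidence, and the laboratory and ECG summaries do not use the TEAE definition.
- A reader might infer that a withdrawal caused by such an event would go unseen. It would not: the general listings and the disposition summary still show it. Protocol 5.5 also has AE as a discontinuation reason and requires the eCRF to be completed and the event followed up.
- A reader might put the size at 1/8 = 12.5 percentage points of an arm's TEAE incidence. That is the weight of any one subject in any arm of 8 and says nothing about how often this gap bites. The denominator can also exceed 8, since up to 14 replacement subjects may be dosed.

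It is also fair to say that the consequence is limited. Safety is not among the listed objectives or endpoints, and no hypothesis test or stopping rule uses TEAE incidence.

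**Conclusion.** The point holds in a narrow form. Followed literally, the onset-only definition can omit an AE recorded between consent and dosing that worsens after dosing from the TEAE incidence tables in protocol 5.9.8.1 and SAP 7.7.1. If the event is non-serious, it can also be omitted from the listing of TEAEs leading to withdrawal. For pre-existing medical-history conditions the omission is possible but not certain.

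This rests on one assumption: that the site keeps the original onset date when an open AE worsens. The documents neither require nor forbid that. The number of affected events cannot be derived from them. The effect is confined to safety reporting, and no PK or PD endpoint changes. It is a minor point, worth correcting because the remedy is nearly free.

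**What to change.** 1. In protocol 5.7.4.1.1 and SAP 7.7.1, define a TEAE as an AE that starts after dosing, or one present before dosing that becomes more severe or more frequent afterwards.
2. State that, for TEAE classification, a worsened event is dated at its worsening, and put the same rule in the eCRF guidance. Apply it to AEs opened before dosing and to medical-history conditions alike.
3. Extend the withdrawal listing in protocol 5.9.8.1 and SAP 7.7.1 to all AEs leading to withdrawal, keeping the listing of serious AEs.
4. Reconcile the synopsis, which plans AE incidence, with protocol 5.9.8.1 and SAP 7.7.1, which plan TEAE incidence.

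The cost is a few sentences, a line of eCRF guidance and slightly higher TEAE counts.

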5.7.4.1.2 Adverse Event Reporting

The recording of AEs will begin after the subject signs the informed consent form and will continue until discharge (or early termination). All AEs, whether serious or nonserious and whether or not related to the study drug, must be recorded in the eCRF. Study subjects will be instructed to warn study staff if he or she has any unexpected symptoms. In addition, all subjects will receive a reminder telephone call approximately 24 hours before Check-in.

Any SAE (whether expected or unexpected) must be entered into the eCRF system and reported by facsimile to the medical monitor or designee using the SAE Reporting Form within 24 hours of the investigator or study clinic staff becoming aware of the event. It is the responsibility of the investigator to report all SAEs to the medical monitor, to provide the most complete report possible, and to assess each SAE for its relationship to the study drug. The investigator is responsible for obtaining follow-up information on all SAEs and submitting follow-up SAE data. Any unexpected SAEs must be reported promptly to the investigator's IRB as per the IRB's requirements.

In the event of a fatal or life-threatening SAE, the sponsor will notify the appropriate FDA authorities by telephone or facsimile within 7 calendar days of receipt of the report. The sponsor will follow all 7-day alert reports with a written report within 10 working days of receipt of the case. Serious AE cases that concern nonfatal, nonlife-threatening events that are unexpected and at least possibly related to the study drug will be submitted in writing to the FDA within 10 working days of receipt.

Furthermore, any AEs that are not expected, occur at a higher frequency, or would require modification of the study protocol and/or informed consent must be reported to the FDA within 10 working days.

Adverse events that are assessed by the investigator as possibly or probably related to the study drug will be followed until they resolve or stabilize. All SAEs will be followed until resolution.

5.7.4.1.3 Assessment of Severity

The investigator will assess the severity of each AE using the following scale:

- Mild: The subject is aware of the AE but is still able to perform all activities; minimal or no medical intervention or therapy is required.
- Moderate: The subject has to discontinue some activities due to the AE; minimal or no medical intervention or therapy is required.
- Severe: The subject is incapacitated by the AE and is unable to perform normal activities; significant medical intervention or therapy is required, and hospitalization is possible.

5.7.4.1.4 Assessment of Causality

The investigator will assess the causal relationship/relatedness of each AE to the study drug using the following scale:

- Not Related: Onset of the AE has no reasonable temporal relationship to administration of the study drug, a causal relationship to administration of the study drug is biologically implausible, or the event is attributed to an alternative etiology.
- Unlikely Related: Onset of the AE has a reasonable temporal relationship to study drug administration and although a causal relationship is unlikely, it is biologically plausible.
- Possibly Related: Onset of the AE has a strong temporal relationship to administration of the study drug, cannot be explained by the subject's clinical state or other factors, and a causal relationship is biologically plausible.
- Probably Related: Onset of the AE shows a distinct temporal relationship to
 administration of the study drug that cannot be explained by the subject's clinical
 state or other factors, the AE is a known reaction to the product or chemical group, or
 can be predicted by the product's pharmacology.

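### The four causality levels are neither exhaustive nor, as worded, mutually exclusive, which affects follow-up of nonserious AEs and the TEAE-by-relationship summaries

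*Protocol*

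**What the plan says.** Protocol 5.7.4.1.4 gives the investigator four levels.

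- **Not Related** is met by any one of three conditions: no reasonable timing, or a causal link that is "biologically implausible, or the event is attributed to an alternative etiology".
- **Unlikely Related** needs reasonable timing and, "although a causal relationship is unlikely, it is biologically plausible".
- **Possibly Related** needs strong timing and an event that "cannot be explained by the subject's clinical state or other factors, and a causal relationship is biologically plausible".
- **Probably Related** starts from distinct timing and then runs on as a comma list, "state or other factors, the AE is a known reaction to the product or chemical group, or" predictable from the pharmacology.

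Protocol 5.7.4.1.2 attaches two actions to the rating. AEs judged "possibly or probably related to the study drug will be followed until they resolve or stabilize". Nonfatal, non-life-threatening SAEs that are "unexpected and at least possibly related to the study drug will be submitted in writing to the FDA" within 10 working days.

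SAP 7.7.1, like Protocol 5.9.8.1, has TEAE incidence "summarized by seriousness, severity, relationship to treatment, and by treatment at onset of the TEAE".

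**The concern.** A causality scale should give each event one level. This one has no place for the common judgement that the drug or something else could be responsible and the two cannot be separated. Possibly Related, where most scales put that judgement, is closed to it because other explanations must be excluded. The investigator must then either state that a drug cause is unlikely, or attribute the event elsewhere, without believing either.

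Such events are foreseeable here. Protocol 5.1.3 lists nasopharyngitis and influenza as common reactions for both drugs, and upper respiratory infection and back pain for evolocumab. All have everyday causes in healthy volunteers followed for 42 to 84 days. The same section describes COVID-19 triage and testing, so competing infectious explanations are expected.

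At stake are the follow-up of nonserious events still present at discharge and the reliability of the split by relationship.

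**Working it through.** The plan states no figure on this point, so there is none to reproduce. The check is of logic.

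**Step 1. Enumerate the event profiles.** Five features drive the definitions:

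- timing (none, reasonable, strong, distinct): 4 levels
- other causes (ruled out, possible, attributed): 3 levels
- plausibility and known reaction combined, where a known reaction implies plausibility: 3 combinations
- causal link judged unlikely (yes, no): 2 levels

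That gives 4 × 3 × 3 × 2 = 72 profiles. Each was tested against the four definitions under two readings of Probably Related. In the disjunctive reading any item in the list is enough. In the conjunctive reading the event needs distinct, otherwise unexplained timing and must also be known or predictable.

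| Reading of Probably | Meets both Not and Probably | Meets more than one level | Meets no level |
|---|---|---|---|
| Disjunctive | 14 of 72 | 28 of 72 | 4 of 72 |
| Conjunctive | 0 of 72 | 11 of 72 | 8 of 72 |

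These counts describe the wording. They are not expected event frequencies.

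**Step 2. The hole.** Take strong or distinct timing, a plausible mechanism, another cause possible but not established, and no judgement that the drug is unlikely.

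- Possibly fails, because another factor could explain the event.
- Unlikely fails, because nobody judges the link unlikely.
- Not Related fails, because timing and plausibility are present and the event is not attributed elsewhere.
- Probably fails on the conjunctive reading. On the disjunctive reading it is met only if the event is a known reaction.

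Events with reasonable but not strong timing, plausible and not judged unlikely, also fit no level, with the same exception for a known reaction read disjunctively.

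**Step 3. The overlap.** Nasopharyngitis attributed to a sick contact is Not Related through the alternative-etiology clause. Read disjunctively, it is also Probably Related as a listed reaction. The conjunctive reading removes that collision, but 11 profiles still meet more than one level. An example is a plausible event attributed elsewhere and judged unlikely, which meets both Not and Unlikely.

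**Step 4. Trace the rating through the rules.**

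| Rule (Protocol) | Uses the rating? |
|---|---|
| Follow-up of nonserious AEs (5.7.4.1.2) | Yes |
| Follow-up of SAEs (5.7.4.1.2) | No, all are followed |
| Follow-up of AEs leading to discontinuation (5.5) | No |
| 24-hour SAE report to the medical monitor (5.7.4.1.2) | No |
| IRB report of unexpected SAEs (5.7.4.1.2) | No |
| 7-day notice of fatal or life-threatening SAEs (5.7.4.1.2) | No |
| 10-working-day report to FDA, first sentence | Yes |
| 10-working-day report to FDA, next paragraph, AEs that are not expected | No |

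An unexpected nonfatal SAE rated Unlikely fails the first 10-working-day sentence but meets the second, with the same deadline. The rating alone therefore decides follow-up only for nonserious AEs that do not lead to discontinuation. All AEs are recorded until discharge whatever their rating, so in practice this concerns events still ongoing at Day 42, 56 or 84.

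**Step 5. Effect on the table.** With 8 subjects per arm (Protocol Table 5-1), moving one subject into or out of the related category changes that arm's related incidence by 1/8 = 12.5 percentage points.

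**The case against.** The strongest reply is that this is a wording flaw with narrow consequences. Several stronger readings might be inferred, and the documents do not support them.

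- *Expedited reports are missed.* The 24-hour, IRB and 7-day rules have no causality condition. The paragraph after the causality-conditioned FDA sentence sends AEs that are not expected to FDA within the same 10 working days. What stands is that the two sentences differ in scope.
- *Follow-up is lost in general.* SAEs and AEs leading to discontinuation are followed whatever the rating. Only the remaining nonserious events are exposed.
- *The scale flatly contradicts itself.* The Not/Probably collision needs the disjunctive reading. The last item in Probably Related has no subject of its own, so 'or' can naturally join only 'known reaction' and 'predictable', both under the timing condition. The disjunctive reading would let a listed reaction be Probably Related with no temporal link at all, which is odd for the top level. This is fair: the wording is ambiguous, and the contradiction is not certain. The hole in Possibly Related does not depend on that reading, apart from known reactions read disjunctively.
- *The safety tables cannot be interpreted.* TEAE incidence by treatment (including placebo), seriousness and severity does not use the rating. Only the split by relationship is unreliable.

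The primary and secondary PD and PK endpoints are untouched.

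**Conclusion.** The point holds within limits. Neither reading of Probably Related gives levels that are exhaustive and exclusive: 4 or 8 of the 72 logical profiles fit no level, and 28 or 11 fit more than one. The main defect is a stated rule, not a missing detail. It pushes plausible but confounded events towards Unlikely or Not Related.

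Two things are affected: follow-up to resolution or stability of nonserious AEs that do not lead to discontinuation, and the summaries by relationship, where one subject is worth 12.5 points in an arm of 8. How many events would be misplaced cannot be computed from the documents. The conclusion assumes that investigators apply the definitions as written; a site that informally treats confounded events as possibly related would avoid the main problem.

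**What to change.** Reword Protocol 5.7.4.1.4 along these lines:

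- **Not Related:** no reasonable temporal relationship; or biologically implausible; or another cause is established and a drug contribution is judged not plausible.
- **Unlikely Related:** reasonable timing and plausible, but a causal relationship is judged unlikely.
- **Possibly Related:** reasonable timing and plausible, not judged unlikely, whether or not other factors could also explain the event, and not meeting Probably.
- **Probably Related:** distinct timing AND not explained by clinical state or other factors AND (a known reaction OR predictable from the pharmacology).

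Possibly Related must not require that another explanation exists. If it did, a new, unexplained and plausible reaction that is neither known nor predictable would fit neither Possibly nor Probably.

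Running the same 72 profiles through this text, with a drug contribution counted as plausible whenever the causal link is, leaves none without a level and 1 with two. That one meets every condition for Probably yet is judged unlikely. Adding 'not judged unlikely' to Probably removes it, and every profile then fits exactly one level.

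Also reconcile the two 10-working-day FDA sentences in 5.7.4.1.2, one conditioned on at least possible relatedness and the other not, so that their scopes agree.

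The cost is protocol wording and a line in the eCRF completion guidance. The downside is a few more events rated possibly related, and so followed up.
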